### **Methods and analysis**

This will be a prospective, observational study that includes patients undergoing elective cardiovascular surgery with cardiopulmonary bypass (CPB). Microcirculation will be quantified with sublingual incident dark field videomicroscopy. Mitochondrial respiration will be measured by performing a substrate-uncoupler-inhibitor titration protocol with high resolution respirometry on peripheral blood mononuclear cells at baseline and serial timepoints during resuscitation and at recovery as a possible liquid biomarker. Plasma samples will be preserved for future analysis to examine endothelial injury and other mechanisms of microcirculatory dysfunction. Thirty-day ventilator and vasopressor-free days (VVFDs) will be measured as a primary outcome, along with sequential organ failure assessment scores, and other clinical parameters to determine if changes in microcirculation and mitochondrial respiration are more strongly associated with clinical outcomes compared to traditional resuscitation targets.

This will be the first prospective study to examine both microcirculatory and mitochondrial function in human patients with circulatory shock undergoing cardiac bypass and address a key mechanistic knowledge gap in the cardiovascular literature. The results of this study will direct future research efforts and therapeutic development for patients with shock.

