## Materials and methods

### Study objective

The primary objective of the MicroRESUS study is to evaluate the microcirculatory and mitochondrial function in patients following elective cardiovascular surgery with cardiopulmonary bypass, to determine if these parameters outperform traditional biomarkers and global hemodynamic measurements to predict clinical outcomes.

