### Incident Dark Field Microscopy

Sublingual microcirculation imaging will be performed using handheld incident dark field (IDF) videomicroscopy (CytoCam, Braedius Medical BV, the Netherlands) at four time points during the enrollment period. Imaging will be performed by the Principal Investigator or trained research personnel. Video sequences are obtained by placing the CytoCam device in the sublingual space and maneuvered so that pressure and motion do not result in image artifact (**Error! Reference source not found.**). A series of successive video clips (3-5 clips of at least 120 frames or 6 seconds in length) should be captured in distinct areas of the sublingual space to account for vessel heterogeneity. Focus and lighting during video capture may be adjusted to optimize image acquisition. Baseline ( $T_{0h}$ ) imaging will be obtained in the preoperative area prior to surgery on the day of the scheduled operation. Repeated measurements will be obtained upon arrival to the ICU (0-2 hours after surgery,  $T_{2h}$ ), during ongoing resuscitation (2-4 hours post-op,  $T_{4h}$ ), and on post-operative day one after recovery ( $T_{24h}$ ).

**Fig 2. A. Experimental setup with patient in supine position during IDF measurement. B. Anatomical sublingual triangle where measurements are obtained.**

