#### Biological samples

Blood gas samples will be drawn into a commercial, pre-heparinized 1 mL blood sampler then immediately analyzed by an ABL90 FLEX automatic blood gas analyzer (Radiometer America Inc., Brea, California, USA). Arterial blood gas samples will be obtained by clinical staff every 1-2 hours for the first 6 hours after ICU admission based on current clinical practice. Central venous blood gas measurements will also be obtained by the study team at the time of microcirculation measurement. Hemoglobin, hematocrit, pH, PaO2, PaCO2, and glucose are also reported on each blood gas analysis. After 6 hours, blood gas analysis will be performed as needed by the clinical team. For biomarker and mitochondrial function analysis, enrolled patients will undergo phlebotomy with volumes of 15 mL drawn into K2EDTA tubes. Blood samples will then be centrifuged at room temperature using Ficoll-PaqueTM PLUS (GE) and Leucosep tubes (Greiner Bio-one). Plasma specimens will be stored at -80°C for later evaluation of the mechanisms of microcirculatory dysfunction. Peripheral blood mononuclear cells (PBMCs) will undergo further analysis and processing as detailed below.

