### Outcome measures

Our hypothesis is that patients with poor post-operative sublingual functional capillary density (defined as a PVD < 22 mm/mm^2 and MHI > 0.4) will have a higher degree of postoperative cardiovascular and pulmonary organ injury compared to patients with normal postoperative microcirculation. The primary outcome for this study will be VVFDs during the first 30 days after surgery. This outcome was chosen because our elective cardiac surgery patients are managed using early recovery after surgery (ERAS) protocols, with a goal to be extubated and weaned off vasopressors within 24 hours after surgery [21,22]. VVFDs will be calculated as a reverse count of consecutive days without requiring ICU-level respiratory or vasopressor support (**Error! Reference source not found.**). Our research group has used a similar primary outcome in a previous clinical trial [23]. The day of operation (day zero) will not be included as all patients undergoing cardiovascular surgery with CPB require mechanical ventilation and vasoactive medications on the day of surgery. Ventilator days will include mechanical ventilation via endotracheal tube or tracheostomy, high-flow nasal cannula  $\geq$  40 liters/minute with an FiO2 > 40%, or non-invasive positive pressure ventilation not prescribed at home. Non-invasive positive pressure ventilation and HFNC will be included as these both require the patient to remain in our ICU. Vasoactives include epinephrine, norepinephrine, vasopressin, phenylephrine, dobutamine, or milrinone at any dose. Subjects in need of respiratory or vasopressor support on day 30, or die before day 30 will be assigned zero VVFDs. If the patient is discharged prior to hospital day 30 a “last status carried forward” approach will be used. Secondary outcomes will include sequential organ failure assessment (SOFA) score on day 1, day 3, diagnosis of acute kidney injury (defined as an increase in serum creatinine  $\geq$  0.3 mg/dL within 2 days), and hospital length of stay.

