**Fig 3. Examples of VVFD scenarios to determine clinical outcomes.**

Exploratory outcomes will examine the relationship of microcirculatory function with common clinical biomarkers such as lactate,  $SvO_2$ , venous-to-arterial  $PCO_2$  gap, capillary refill time, and lactate to pyruvate ratio. Markers of endothelial injury and inflammation such as soluble vascular cell adhesion molecule 1 (sVCAM-1), soluble intercellular adhesion molecule 1 (sICAM-1), e-selectin, IL-8, IL-10, and other inflammatory cytokines will be measured. We will also examine mitochondrial complex function in human blood cells, comparing individual complex (I, II, III, and IV) function and reactive oxygen species generation between patients with and without post-operative shock.

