### Statistical and analysis plans

Continuous variables characterizing demographical data, microcirculation data, and mitochondrial respiration measurements, and outcomes data will be reported as means with standard deviations if normally distributed or medians with interquartile ranges if not normally distributed. Categorical variables will be represented as frequencies and proportions. To examine the predictive performance of selected variables for the primary outcome, we will construct receiver operator characteristic curves for threshold values of PVD, MHI, lactate,  $SvO_2$ , mean arterial pressure, and cardiac index. A Youden index will be calculated to determine the best cutoff value for determining prolonged VVFDs.

Linear regression modeling will be used to examine the relationship between L/P ratio and postoperative microcirculation variables. We will perform univariate analyses on candidate predictor variables of L/P ratio including PVD, MHI, LFTs, creatinine, CPB time, cross clamp time, and catecholamine administration. Multiple linear regression analysis will be used to model the effect of significant predictors. Repeated measure ANOVA will be used to compare changes in microcirculatory variables, mitochondrial respiration, and mitochondrial reactive oxygen species production over time. To adjust for multiple comparisons, post-hoc pairwise Tukey Kramer t-tests will be performed. All analyses will use statistical software (SAS version 15.1, Cary, NC; Prism v 9.0, Graph-Pad Software, San Diego, CA).

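### The objective asks whether microcirculatory and mitochondrial parameters outperform traditional markers, but the plan contains no between-marker contrast on VVFDs and relates no mitochondrial variable to VVFDs

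*Combined protocol and SAP*

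**What the plan says.** The Study objective section states the aim as "to determine if these parameters outperform traditional biomarkers and global hemodynamic measurements to predict clinical outcomes". The abstract repeats it, asking whether "changes in microcirculation and mitochondrial respiration are more strongly associated with clinical outcomes compared to traditional resuscitation targets".

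The section Statistical and analysis plans answers this for VVFDs as follows: "we will construct receiver operator characteristic curves for threshold values of PVD, MHI, lactate", SvO2, mean arterial pressure and cardiac index. It then adds: "A Youden index will be calculated to determine the best cutoff value for determining prolonged VVFDs". The regression models in that section have the lactate-to-pyruvate ratio as outcome, not VVFDs.

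Mitochondrial measurements appear in descriptive summaries, in a repeated-measures ANOVA over time, and among the exploratory outcomes, which involve "comparing individual complex (I, II, III, and IV) function and reactive oxygen species generation between patients with and without post-operative shock".

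Sample size and power implies one further analysis of VVFDs: a one-sided t-test between high and low PVD groups.

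Imaging takes place before surgery, twice in the first four postoperative hours, "and on post-operative day one after recovery". Systemic data are collected at ICU admission and then hourly for six hours.

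**The concern.** A claim that one marker outperforms another is a claim about a difference. Separate ROC curves on the same patients give one AUC per marker. They give neither an estimate of the difference nor its uncertainty, which depends on how the markers correlate within patients. The remaining step would be to rank point estimates by eye.

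Two further gaps affect the ROC analysis itself.

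- **Outcome class.** VVFDs are a count from 0 to 30, whereas an ROC curve needs two classes. The Youden index selects a cutoff on the marker and cannot define the outcome class. The label used for that class is also unclear in direction, because more free days is the better result.
- **Reading time.** There are three postoperative imaging times and several hourly systemic readings, and the plan does not say which enters each curve.

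At stake is the headline conclusion. The PVD group comparison could still be made, but a statement that microcirculatory or mitochondrial measures beat lactate or hemodynamics would have no planned analysis behind it.

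**Working it through.** **1. Objective against analysis.**

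| Element of the objective | Planned analysis on VVFDs |
|---|---|
| Microcirculation predicts outcome | ROC for PVD and MHI; t-test by PVD group implied by the sample-size section |
| Traditional markers predict outcome | ROC for lactate, SvO2, mean arterial pressure, cardiac index |
| Difference between the two sets | None stated |
| Mitochondrial function predicts outcome | None stated |
| Mitochondrial function against traditional markers | None stated |

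Fig 1, Fig 3 and S1 Appendix are not visible, so this is limited to the text available.

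**2. The plan's own figure.** The 134 rests on a two-group mean difference, not on an AUC. The SD is not in the visible text. Solving n = 2(z_0.95 + z_0.80)² SD² / δ² with n = 67 per group and δ = 2 days gives SD = 2 / [(1.645 + 0.842) × √(2/67)] = 4.66 days (4.63 by exact t-test). This reads the stated β of 0.8 as power. The figure is coherent for the PVD comparison and says nothing about precision for a marker contrast.

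**3. Precision of the missing contrast.** The following are assumptions: both AUCs 0.65, correlation r from 0.3 to 0.6, and 25% to 40% of patients in the poor-outcome class. That share is borrowed from the rate of shock and organ injury in the Background, a different quantity. Because Outcome measures sets a goal of weaning within 24 hours, a share of 10% is also shown.

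The Hanley-McNeil variance is [A(1−A) + (n1−1)(Q1−A²) + (n0−1)(Q2−A²)] / (n1·n0), with Q1 = A/(2−A) = 0.4815 and Q2 = 2A²/(1+A) = 0.5121. For 34 events and 100 non-events:

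- variance = [0.2275 + 33 × 0.0590 + 99 × 0.0896] / 3400 = 0.00325, so SE = 0.0570
- 95% half-width of the difference = 1.96 × 0.0570 × √(2(1−r)) = 0.132 at r = 0.3 and 0.100 at r = 0.6

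With 54 events (40%) the SE is 0.0491 and the half-widths are 0.114 and 0.086. With 13 events (10%) the SE is 0.0862 and they are 0.200 and 0.151. Here r is the correlation between the AUC estimates. Simulation with normal markers correlated 0.3 to 0.6 within class, and DeLong standard errors, gives slightly smaller values: about 0.09 to 0.13 at 25% to 40%, and 0.14 to 0.19 at 10%.

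**4. What ranking by eye would do.** With equal true AUCs of 0.65 and 25% to 40% events, PVD's point AUC leads one given rival by more than 0.05 in about 12% to 22% of simulated studies. The 0.05 gap is only a yardstick; the plan does not use it.

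**5. What a formal contrast could show.** If PVD truly had AUC 0.75 against 0.65, a named contrast would be supported after Holm over four comparisons in about 24% to 53% of studies at 25% to 40% events, and in about 12% to 19% at 10%. These figures move by a few points between simulation runs.

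**6. Youden index.** For a true AUC of 0.65 at 25% to 40% events, the apparent index averages 0.28 to 0.30, against 0.19 to 0.20 true at the chosen cutoff. For a useless marker the apparent index averages about 0.11 (40% events) to 0.17 (10% events), against a true 0.

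**The case against.** The strongest reply is that this is a single-center observational study whose powered hypothesis concerns PVD groups, so the ROC curves are descriptive support. Part of that stands. A reader might infer that ROC curves are the only planned look at VVFDs, or that the study can answer nothing. Neither is supported, because the t-test implied by Sample size and power addresses PVD. It does not compare PVD with any rival, however, and the comparative aim is stated as primary, not exploratory.

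Other stronger readings also go beyond the documents:

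- **T24h overlap.** That imaging falls on postoperative day one, which counts toward the outcome, since "The day of operation (day zero) will not be included". Nothing assigns T24h to the ROC curves, so the overlap arises only if that reading is used.
- **Choices made after seeing outcomes.** Status and timeline of the study announces a preliminary analysis that includes VVFDs. It does not say that ROC curves or cutoffs are part of it.
- **Change scores.** The abstract's reference to changes may mean abnormalities rather than differences from baseline, so a missing change-score analysis is not a clear defect.
- **A false-claim rate.** The 12% to 22% in step 4 is not one, because the plan has no rule that turns a lead into a claim. It is also not comparable with the roughly 2% (25% to 40% events) to 4% (10% events) of studies making any false claim under Holm.
- **A mitochondrial contrast from existing data.** Respirometry hours are not given in the visible text, and Risk Assessment limits blood collections to two in a week. Matching samples may not exist.

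**Conclusion.** The concern holds in this form and the analysis section should be changed. In the text available, the comparative claim and the mitochondrial half of the primary objective have no analysis on VVFDs that could support or reject them. The outcome threshold, its direction and the reading time are also unstated. This conclusion comes from reading the sections together and does not depend on the simulations.

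The size is less certain. The half-widths, power and Youden figures rest on assumed AUCs, correlations and event shares; only the 134 comes from the plan. Across those assumptions the precision is modest at best, so a correct analysis may well be inconclusive.

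**What to change.** In Statistical and analysis plans:

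1. Report the paired difference in AUC, or in a concordance index on the full VVFD count (which needs no threshold), between the microcirculatory marker and each of lactate, SvO2, mean arterial pressure and cardiac index. Give 95% intervals by DeLong or paired bootstrap and a stated multiplicity rule such as Holm. Claim superiority over a named marker only when that contrast supports it. State whether the primary marker is PVD alone, as in Sample size and power, or PVD with MHI, as in Outcome measures. State whether SvO2 is mixed venous (eligibility criteria and Physiologic and pharmacologic data) or central venous (list of abbreviations).
2. Fix one early postoperative time before T24h, and use each rival's reading nearest to imaging. For blood gases this is practicable: "Central venous blood gas measurements will also be obtained by the study team at the time of microcirculation measurement". Mean arterial pressure and cardiac index would come from the hourly record. If ROC is kept, state the VVFD threshold and its direction. Fix all of this before marker-outcome results are examined, and say whether the preliminary analysis has already been done.
3. Either add one named mitochondrial parameter with the same contrasts as a secondary analysis, provided existing samples supply it at a matching time, or limit the outperform objective to microcirculatory markers.
4. Label Youden cutoffs exploratory and report optimism-corrected values.

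**Cost.** Items 1, 2 and 4 need plan wording and a short program. Item 3 depends on which samples exist. The price is candor about wide intervals. The concordance option may be somewhat tighter (half-width about 0.06 to 0.09 under two assumed skewed VVFD distributions). In simulation, bootstrap correction removed only about 60% to 75% of the Youden overstatement, so the cutoffs would remain exploratory.

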## **Sample size and power**

Using data from our previous foundational work as well as unpublished pilot data, we anticipate a 1:1 allocation of patients to the high ( $PVD > 22\text{mm/mm}^2$ ) and low group ( $PVD \leq 22\text{ mm/mm}^2$ ). We will need a sample size of at least 134 subjects to detect at least a 2-day difference in ventilator and vasopressor-free days (VVFDs) with a  $\beta=0.8$ , using a one-sided t-test  $\alpha=0.05$  [5,6]. We will enroll a total of 140 subjects to allow for a 5% loss to follow-up (surgical delay, ICU delay, cancelled surgery, etc.) and exclusion due inadequate microcirculation video quality (S1 Appendix).

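### Sensitivity, specificity and J at each Youden-selected cutoff will be overstated, because the cut is chosen and scored in the same patients with no optimism correction

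*Combined protocol and SAP*

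**What the plan says.** Under Statistical and analysis plans, ROC curves are planned for PVD, MHI, lactate, SvO2, mean arterial pressure and cardiac index to examine how well they predict the primary outcome. The cut comes next: "A Youden index will be calculated to determine the best cutoff value for determining prolonged VVFDs". The section mentions no resampling, split sample or external data, and no confidence interval for a cut or its accuracy. The only adjustment it names is Tukey-Kramer for pairwise comparisons, which does not bear on cutoff selection.

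The data are one single-centre cohort (Study design and setting). Sample size and power gives its size: "We will need a sample size of at least 134 subjects to detect at least a 2-day difference", and "We will enroll a total of 140 subjects to allow for a 5% loss to follow-up".

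Two microcirculation definitions are fixed in advance. Sample size and power splits patients at a PVD of 22 mm/mm². The hypothesis under Outcome measures, about "patients with poor post-operative sublingual functional capillary density", uses PVD below 22 together with MHI above 0.4. The ROC paragraph does not refer to either. No section says what number of VVFDs counts as prolonged.

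**The concern.** A Youden cut is a maximum taken over every possible cut in the sample. Chance variation that favours one cut over its neighbours is selected along with any real signal. Sensitivity, specificity and J computed at that cut in the same patients therefore look better, on average, than they would in new patients.

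What is at stake is the stated performance of the proposed thresholds. The abstract expects the results to direct later research and therapeutic development. A threshold reported with uncorrected accuracy would tend to disappoint when applied elsewhere, and a reader would have no means of judging by how much.

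**Working it through.** **1. The plan's own figures.** The documents give no expected AUC, J or sample size for the ROC analysis, so there is no accuracy figure to reproduce. The 134 belongs to the t-test on VVFDs. No SD is printed, so it cannot be reproduced directly, but the implied SD can be found. I read the printed β = 0.8 as power and use one-sided α = 0.05 and 67 per group:

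n per group = 2(1.645 + 0.842)² SD² / 2², so 67 = 3.09 SD² and SD ≈ 4.66 days.

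For losses, 140 × 0.95 = 133, close to 134. I therefore use n = 134; with n = 140 the results for a useless marker are almost the same.

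**2. Assumptions the documents do not supply.** The share of patients with prolonged VVFDs is varied from 10% to 50%. Markers are normal with equal variance. Non-cases follow N(0, 1) and cases N(d, 1), with d = √2 Φ⁻¹(AUC). The direction of each marker is fixed in advance.

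**3. Quantities compared.**
- Apparent J = maximum over cuts c of [sensitivity(c) + specificity(c) - 1] in the sample.
- True J at the chosen cut = Φ(d - c) - Φ(-c), the value expected in new patients.
- Optimism = apparent J minus true J.

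As a check on scale, the best J attainable is 2Φ(d/2) - 1. For AUC 0.70, d = 0.742 and this is 0.289. For AUC 0.60, d = 0.358 and it is 0.142.

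**4. Results** (simulation, 20,000 data sets per cell, n = 134; apparent J / true J at the chosen cut / optimism):

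| Events | No value (AUC 0.50) | AUC 0.60 | AUC 0.70 |
|---|---|---|---|
| 15% (20 cases) | 0.142 / 0 / 0.142 | 0.254 / 0.121 / 0.133 | 0.383 / 0.264 / 0.119 |
| 25% (34 cases) | 0.117 / 0 / 0.117 | 0.230 / 0.124 / 0.106 | 0.363 / 0.269 / 0.094 |
| 50% (67 cases) | 0.102 / 0 / 0.102 | 0.217 / 0.126 / 0.091 | 0.351 / 0.272 / 0.079 |

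At 10% events (13 cases) the optimism rises to about 0.17, 0.16 and 0.15 respectively. Rarer events mean more optimism. At AUC 0.60 with 25% events, 0.106 / 0.230 = 46% of the apparent J is optimism.

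**5. AUC in the same simulations.** The mean empirical AUC was 0.50, 0.60 and 0.70 for true values of 0.50, 0.60 and 0.70. The bias arises in choosing the cut, not in the curve.

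**6. What bootstrap correction recovers** (300 data sets, 200 resamples each, 25% events). For a marker with no value, J falls from 0.118 to 0.043 (true value 0). For AUC 0.70 it falls from 0.358 to 0.294 (true value 0.269). The share of bias removed is (0.118 - 0.043) / 0.118 = 64% and (0.358 - 0.294) / (0.358 - 0.269) = 72%.

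**The case against.** Several points on the other side are sound and limit the concern.

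- **Comparison of markers.** The primary objective asks whether microcirculatory and mitochondrial measures predict better than traditional ones. Optimism falls on every marker and largely cancels in a comparison. At 25% events the apparent gap in J between AUC 0.70 and 0.60 is 0.363 - 0.230 = 0.133, against 0.269 - 0.124 = 0.145 in new patients. This stands: the harm is to absolute accuracy at a cut, much less to the ranking.
- **Useless markers.** A reader might infer that a worthless marker will look informative. On average it does not. At 30% events it shows about 58% sensitivity and 53% specificity, with a mean AUC of 0.50. Taking the best of six makes this worse, but a calculation for six independent markers does not fit here: PVD and MHI come from the same videos, and the plan states no rule for naming a winner.
- **The VVFD group comparison.** A reader might also infer that Youden cuts will define the groups whose VVFDs are compared, inflating the type I error. The documents plan no such step. The sample-size comparison uses a PVD cut fixed in advance and is unaffected.
- **Prespecified cuts.** A PVD ROC curve contains the point at 22, so the plan does not exclude reporting accuracy there. It does not commit to it either. MHI 0.4 appears only jointly with PVD, and the other four markers have no cut fixed for the ROC analysis.

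None of this removes the bias in sensitivity, specificity and J at a Youden cut.

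**Conclusion.** The concern holds for accuracy at the selected cut and no further. Followed as written, the plan would overstate J by about 0.08 to 0.15 at a true AUC of 0.70, 0.09 to 0.16 at 0.60, and 0.10 to 0.17 for a marker with no value. These ranges assume 134 patients, normal markers of known direction and an event share of 10% to 50%. That share is an assumption because prolonged VVFDs are undefined, a gap that must be closed before any ROC curve can be drawn. S1 Appendix, cited under Sample size and power, was not in the text available and could not be checked.

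The change is worth making. It does not call into question single-marker AUCs or the prespecified PVD comparison.

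**What to change.** 1. Define prolonged VVFDs before analysis, with both threshold and direction. VVFDs count days free of support, so a high value is the good outcome and the term can be read either way.
2. Make AUC with a confidence interval the main measure for comparing the six markers, with each marker's direction fixed in advance.
3. Report sensitivity and specificity at the prespecified PVD cut of 22 mm/mm² and, separately, for the joint definition of PVD below 22 with MHI above 0.4. These carry no cutoff-selection bias.
4. For every Youden cut, repeat the whole selection in at least 1000 bootstrap samples. Report optimism-corrected sensitivity, specificity and J, with an interval for the cut itself.
5. Label the Youden cuts exploratory.

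The cost is a few sentences in the analysis plan and a short program; no new data are needed. Reported accuracy will look slightly less favourable. The bootstrap also leaves some bias, about 0.02 to 0.04 in J in the 25%-event checks above (0.294 - 0.269 = 0.025; 0.043 - 0 = 0.043), and the report should say so.

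### The ROC analysis cuts the 0-30 day VVFD count in two; a concordance index on the full count should lead the comparison of markers

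*Combined protocol and SAP*

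**What the plan says.** All sections cited are in the combined protocol and SAP.

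- **Study objective.** The microcirculatory and mitochondrial measures are studied "to determine if these parameters outperform traditional biomarkers and global hemodynamic measurements to predict clinical outcomes".
- **Outcome measures.** "The primary outcome for this study will be VVFDs during the first 30 days after surgery". The scale is a count: "VVFDs will be calculated as a reverse count of consecutive days without requiring ICU-level respiratory or vasopressor support". Patients still on support at day 30 score zero, as do those who "die before day 30 will be assigned zero VVFDs".
- **Statistical and analysis plans.** "To examine the predictive performance of selected variables for the primary outcome, we will construct receiver operator characteristic curves", for PVD, microcirculatory heterogeneity index (MHI), lactate, SvO2, mean arterial pressure and cardiac index. Then: "A Youden index will be calculated to determine the best cutoff value for determining prolonged VVFDs". The other models in that section have different outcomes: linear regression is for the lactate-to-pyruvate ratio, and repeated-measures ANOVA is for microcirculatory and mitochondrial variables over time.
- **Sample size and power.** At least 134 subjects are needed to detect a 2-day VVFD difference between high and low PVD groups in a one-sided t-test at 0.05. This comparison is not listed in the analysis section.

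**The concern.** The outcome has up to 31 ordered values, and the planned predictive analysis keeps two. Every patient on the same side of the line becomes equal, so the analysis cannot use the difference between a death and a slightly slow recovery. The answer also depends on where the line falls. The visible text gives no day for *prolonged* and no direction, although fewer VVFDs is the worse outcome.

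The Youden index chooses a cutoff on the marker, not on VVFDs, but it still presupposes a binary VVFD state. At stake is the precision with which each marker's accuracy, and each difference between markers, is estimated from about 134 patients. The comparison of new with traditional markers is the stated objective, and MHI, lactate, SvO2, mean arterial pressure and cardiac index have no full-count analysis anywhere in the documents.

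**Working it through.** **1. The plan's own figure.** Inputs from Sample size and power: 2 days, 67 per group, one-sided 0.05, power 0.8 (printed as beta, read here as power). The visible text gives no SD, so it is solved for.

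- Normal formula: 67 = 2 × (1.645 + 0.842)² × SD² / 2², giving SD of about 4.66.
- Noncentral t: SD = 4.63.

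The 134 is therefore reproduced if the SD is about 4.65, but cannot be confirmed independently.

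**2. Marker strength on a normal outcome.** Standardised difference d = 2 / 4.63 = 0.432. Point-biserial r = 0.432 / √(0.432² + 4) = 0.211. Undoing the median split of the marker: 0.211 / 0.798 = about 0.265.

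**3. Why 0.265 is too weak for a ceiling-heavy count.** Assume 3% zeros; 30%, 50% or 70% of patients at 30 days; and the rest losing days on an exponential-type scale with parameter 3. A latent correlation of 0.265 then gives a high-versus-low PVD difference of only about 1.7, 1.6 and 1.4 days. Reaching the protocol's 2 days needs about 0.31, 0.33 and 0.39.

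**4. Power at the 2-day effect.** Simulation with n = 134, one-sided 0.05 and 1,500 trials per setting, comparing rank concordance on the full count with the ROC area (Mann-Whitney) after cutting. Power in %, loss in points in brackets.

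| At 30 days | Full count | Cut at ceiling (29 or fewer) | 28 or fewer | 27 or fewer | 25 or fewer |
|---|---|---|---|---|---|
| 30% | 95 | 84 (11) | 87 (8) | 86 (9) | 80 (15) |
| 50% | 97 | 92 (5) | 91 (6) | 89 (8) | 80 (17) |
| 70% | 98 | 97 (1) | 95 (3) | 91 (7) | 82 (16) |

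Simulation error on a power of 80% is √(0.8 × 0.2 / 1500), about 1 point. A repeat with 4,000 trials per setting gave losses of about 1 to 16 points, which is the range used here.

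**5. Sensitivity.**

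- *Weaker effect (correlation 0.265).* 30% at ceiling: 88 versus 67-77. 50%: 85 versus 77, 76, 72 and 63 at the four cuts. 70%: 78 versus 75, 70, 66 and 55. Losses run from 78 − 75 = 3 to 78 − 55 = 23 points.
- *Other shapes.* A separate set of 120 settings (correlation 0.20-0.30; 12-75% at ceiling) gave losses of about 1 to 45 points for monotone effects. The median was 29 when 10% or fewer were classed as prolonged, and 12 when 35-55% were.
- *Marker contrasts.* A marker with correlation 0.3 against an uninformative one lost 3 to 40 points.
- *Reversal.* If the marker acts only on crossing one VVFD threshold and the cut sits exactly there, cutting gains 10 to 29 points. One day to either side, the result ranged from an 8-point gain to a 19-point loss.
- *Type I error.* It was 0.05-0.06 for the concordance test, so the gap does not come from a liberal test.

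**The case against.** - **A full-count analysis is already implied.** A reader might infer that ROC is the only VVFD analysis in the study. The documents do not support that: the study is sized on a t-test of the count between PVD groups. This stands, and it limits the point to predictive performance and to comparing markers. The t-test covers PVD only and cannot rank PVD against lactate or cardiac index.
- **No test of any ROC area is planned.** The section states no hypothesis, alpha or power for an area or for a difference between areas, and finding a threshold is a fair bedside aim. This also stands. Power here is a yardstick for information lost, not a shortfall against a stated target.
- **The likely shape favours a small loss.** Patients are managed "with a goal to be extubated and weaned off vasopressors within 24 hours after surgery", and day zero is not counted, so a large group at the ceiling is plausible. A cut at that ceiling with 50-70% of patients there costs only about 1 to 5 points. That is right for that cut, but the plan does not commit to it.
- **Concordance is not a full remedy.** It uses order only: 0 against 29 days counts like 28 against 29. Nor is it equivalent to a proportional-odds model, which adds assumptions of its own.
- **Unseen material.** The S1 Appendix and Fig 3 are not in the text supplied. An SD or a VVFD category may be given there.

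**Conclusion.** The point holds as a cheap improvement. In the analysis section, the only predictive-performance analysis of the primary outcome, and the only marker-VVFD analysis listed, reduces an ordered count to two classes. No planned analysis compares markers on the full count.

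For a monotone effect of the size the protocol plans for, the cost is about 1 to 16 points of single-marker power: least with a cut at a large ceiling group, most with a cut at 25 days or fewer. This rests on the back-solved SD, 3% zeros, 30-70% at ceiling and the assumed shape of days lost, none of which the visible text gives.

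A reader might infer a fixed and substantial penalty whatever the cut, or a study left underpowered. Neither is supported. Dichotomised power stayed at about 80% or more in every setting at the 2-day effect, and cutting can even gain if the effect lies exactly at the cut. The direction is secure for monotone effects; the size is not.

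**What to change.** In Statistical and analysis plans, add one or two sentences:

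- The lead measure of predictive performance is a concordance index (Harrell's c or Somers' D) of each marker with the full 0-30 VVFD count, zeros ranked lowest, with each marker's direction fixed in advance.
- Markers are compared by paired bootstrap differences in that index, with confidence intervals.
- ROC curves and the Youden cutoff are kept as a secondary, descriptive display, with the day and direction that define *prolonged* written down.

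The cost is a few lines of standard code, with no new data or patients. The small downside is that the index gives no sensitivity or specificity at a cutoff, which is why the ROC display stays, and it uses only the order of the outcomes.
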